# 2.2 Secondary Objectives (if applicable)

NA

# 2.3 Exploratory Objective (if applicable)

The exploratory objective is to identify baseline factors (e.g., age, MNSI, general activity) predictive of improvement, represented as the baseline to follow-up change in each outcome. This objective will be addressed using linear regression and bivariate correlations.

# 3 Study Design and Endpoints

# 3.1 Description of Study Design

This single-center, longitudinal design study uses multinuclear-MRI to evaluate the mechanistic effects of exercise on skeletal muscle function and peripheral nerve integrity in patients with DPN, and to determine whether exercise can reverse DPN symptoms. Forty DPN patients will be enrolled and be prescribed a 10-week exercise program following a 4-week non-exercise period. The exercise program will comprise aerobic and resistance components; a moderate level of intensity will be calculated based on results from a maximal graded exercise test (VO2R) conducted prior to the intervention. Multinuclear-MRI data will be acquired at baseline, as well as before and after the intervention that can provide mechanistic insight into the adaptations in lower leg muscle function and peripheral nerve integrity of patients with DPN, and their role in improving DPN symptoms.

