# **Protocol Summary**

Title	A cross-over, single-center study investigating the effects of exercise on reversing diabetic peripheral neuropathy
Short Title	Reversing diabetic peripheral neuropathy through exercise
Brief Summary	This project proposes a longitudinal design that uses multinuclear-MRI to evaluate the mechanistic effects of exercise on skeletal muscle function and peripheral nerve integrity in patients with diabetic peripheral neuropathy (DPN), and to determine whether exercise can reverse DPN symptoms. We will prescribe a 10-week exercise program to 40 DPN patients. We will acquire multinuclear-MRI data before and after the intervention that can provide mechanistic insight into the adaptations in lower leg muscle function and peripheral nerve integrity of patients with DPN, and their role in improving DPN symptoms following physical exercise intervention.
Phase	N/A
Objectives	Objective 1: Determine the effect of exercise on peripheral nerve architecture, function, and symptoms of DPN. Objective 2: Determine the effect of exercise on lower leg muscle structure and function in DPN patients.
Methodology	Longitudinal design
Endpoint	Body mass index (BMI), glycosylated hemoglobin (HbA1c), and C-reactive protein will be assessed before and after the 10-week intervention, along with the following measures of neuropathic symptoms: 1) Michigan Neuropathy Screening Instrument (MNSI) symptom questionnaire and the PROMIS physical function and fatigue questionnaire, 2) MNSI physical exam score, 3) Vibration Perception Threshold (VPT) and Calf Muscle performance, 4) Plasma levels hydrogen peroxide as marker of ROS, 5) Lower leg muscle performance (9-item Physical Performance Test), activity monitor with actigraph, and 6) Multinuclear MRI will assess changes in muscle function and peripheral nerve integrity. 7) Utah Early Neuropathy Scale, which is a physical exam specific to early sensory predominant polyneuropathy.
Study Duration	2 years
Participant Duration	~10 weeks
Duration of behavioral intervention	10 weeks
Population	40 patients with Type 2 diabetes and clinical symptoms of DPN (both male and female) between the ages of 40-70 years old
Study Sites	Single-center
Number of participants	40 participants expected to be enrolled across one site

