# 1.2 Rationale

Hyperglycemia is an important factor in the development of DPN. However, the pathophysiological processes through which hyperglycemia causes DPN are not fully understood. Furthermore, large clinical studies (ACCORD [27], ADVANCE [28], VADT [29]) have shown that good glucose control is insufficient to reduce the occurrence of foot complications, including DPN and diabetic foot ulcers. There are no Food and Drug Administration (FDA)-approved treatment options that target the underlying pathogenesis of DPN [19, 30]. Therefore, it is important to establish strategies to delay or reverse the effects of DPN.

We hypothesize that DPN patients who undergo 10 weeks of exercise will show improved peripheral nerve integrity and function, and that exercise will improve the structure, local metabolic, and MV functions of skeletal muscle. A major obstacle to assessing how DPN affects skeletal muscle and peripheral nerves is the lack of sensitive, objective, and reproducible tests to detect small changes in muscle and nerve functions [10]. Multinuclear-MRI can bring new insights into how DPN affects skeletal muscle (31P)-MRI techniques that can reliably assess skeletal muscle metabolic function [34, 35], as well as rapid

CONFIDENTIAL

This material is the property of the NYU School of Medicine and Langone Medical Center. Do not disclose or use except as authorized in writing by the study sponsor

techniques to quantify blood oxygenation level dependent (BOLD)-MRI signals, sensitive to MV function [36-38] and its adaptations after exercise interventions [39]. In addition, we will use diffusion tensor imaging (DTI), a powerful MRI technique, to quantitatively assess neuronal integrity and detect nerve injury and monitor reinnervation [40-46]. The use of DTI will allow us to non-invasively assess peripheral nerve adaptations after exercise intervention. Finally, we will use IDEAL-MRI to quantify levels of intramuscular adipose tissue (IMAT), which are elevated in DPN [47-50]. We will prescribe a 10-week exercise program, with both aerobic and resistance components [14, 24], to 40 DPN patients who will receive personal supervision from health professionals. We will acquire multinuclear-MRI data at three time points: 1) baseline, 2) pre-intervention and 3) post-intervention. We will measure plasma levels of reactive oxidative species (ROS) as markers of oxidative stress.

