#### CONFIDENTIAL

This material is the property of the NYU School of Medicine and Langone Medical Center. Do not disclose or use except as authorized in writing by the study sponsor Behavioral Intervention Template Version: 5 MAY 2017 If a participant chooses to withdraw from the exercise intervention, they will be contacted by study personnel and reasons for withdrawal will be documented. We will seek written permission to contact participants and will reach them using their preferred method (phone or email). Reasons for withdrawal will be classified as related or unrelated to intervention. Participants will be invited to complete endpoint testing even if they choose to withdraw from the intervention.

Participants that cannot complete the study due to incompatible logistics (precipitating from i.e. covidrelated study suspension or personal leave of absence) will be encouraged to continue the study at a later date. Participants with long-term absences will be re-consented and will re-perform all study procedures in the longitudinal protocol described in section 6. Such participants will be considered newly enrolled and must meet all inclusion/exclusion criteria laid out in section 4. Long-term absence is defined as: 1) greater than 3-months between Step 2: Blood draw (section 6.4.1.2) and Post-non-exercise phase visit (section 6.4.3) or 2) greater than 4-months between Post-non-exercise phase visit (section 6.4.6).

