## 6.4.4 Post-Exercise Phase Visit

Participants will undergo blood tests, VO2R, and a final MRI to compare with results collected prior to the exercise intervention. The final visit should occur within two weeks after the last exercise session. This will allow for feasible scheduling, data collection, and study completion considerations.

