# 9 Statistical Considerations

# 9.1 Statistical and Analytical Plans

The primary objective is to assess and compare the interventions (exercise versus control phase in the same individual) in terms of the baseline to follow-up change in the following outcomes: 1) DTI, plasma ROS level, and the MNSI assessment of DPN symptoms (Aim 1); and 2) leg mitochondrial function, oxidative capacity (31P-MRI), peak MV response (BOLD-MRI), the proportion of fat-free muscle (IDEAL-MRI) and leg muscle strength (Aim 2).

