# 9.3 Description of Statistical Methods

A weighted paired sample *t*-test will be used to assess whether each outcome changed from baseline to follow-up as a result of the exercise intervention. Weighted analysis of covariance (ANCOVA) will be used to compare the time points in terms of the change in each outcome. The change in each outcome from baseline to follow-up will be the dependent variable and the ANCOVA model will include the matching factors (age, baseline MNSI) and the measure of general activity level as numeric covariates and the binary indicator of intervention as a classification factor. The secondary objective is to assess the extent to which exercise induced improvements in DTI outcomes are mediated or explained by reduction in ROS. After testing the effect of the intervention on the change in DTI and the correlation between changes in DTI and ROS, an incomplete causal pathway meditational analysis will be conducted using the method of Baron and Kenny[63] with a bootstrap based test of the indirect (mediation) effect of ROS. The exploratory objective to identify baseline factors (e.g., age, MNSI, general activity) predictive of improvement, represented as the baseline to follow-up change in each outcome, will be addressed using linear regression and bivariate correlations. This analysis will be stratified by intervention and then conducted using data from both intervention groups combined. In each case, the assessment of compliance will be included as a weighting factor.

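### For MRI outcomes, a control change over about 4 weeks is compared with an exercise-phase change over about 13, in fixed order and with no term for elapsed time

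*Combined protocol and SAP*

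**What the plan says.** The Protocol Summary gives the title "A cross-over, single-center study investigating the effects of exercise on reversing diabetic peripheral neuropathy". Section 3.1 describes a single sequence for everyone: "Forty DPN patients will be enrolled and be prescribed a 10-week exercise program following a 4-week non-exercise period". Section 1.2 plans three scans: "We will acquire multinuclear-MRI data at three time points: 1) baseline, 2) pre-intervention and 3) post-intervention".

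Attachment A puts MRI in Weeks 1, 5 and 18, exercise in Weeks 7 to 16, and the VO2R test in Weeks 6 and 17. Section 6.4.4 adds: "The final visit should occur within two weeks after the last exercise session".

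Section 9.1 sets the comparison, which is made on the change in each outcome: "The primary objective is to assess and compare the interventions (exercise versus control phase in the same individual) in terms of the baseline to follow-up". In Section 9.3 a weighted ANCOVA "will be used to compare the time points in terms of the change in each outcome", and its terms are given as: "The change in each outcome from baseline to follow-up will be the dependent variable and the ANCOVA model will include the matching factors". Those factors are age and baseline MNSI; general activity and a binary intervention indicator are added. Nothing represents elapsed time. The same section attributes a baseline to follow-up change to the exercise intervention. Section 9.3.4 gives the control phase a weight of 1, so a control-phase term is clearly intended.

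Other sections differ. Section 9.3.1 has two scans (visits 1 and 3), Section 9.3.2 tests baseline against follow-up without a control-phase contrast, and Section 12.3 pays for two scans.

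**The concern.** Every participant has the untreated phase first, so phase cannot be separated from calendar time, and the two MRI intervals differ in length by a factor of about three. A raw change over 4 weeks estimates what 4 untreated weeks do. It does not show what 13 untreated weeks would have done. If the outcome moves at all without exercise, the phase contrast is not centred on zero when exercise has no effect.

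The sign of the shift depends on the sign of the drift. Section 1.1 speaks of DPN progression; worsening over the extra weeks would mask a real benefit. Favourable drift would do the opposite.

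There is also an asymmetry of test order. The pre-exercise MRI (Week 5) precedes the maximal exercise test (Week 6), while the final MRI (Week 18) follows it (Week 17). What is at stake is the causal reading of the MRI results, which are central to both aims.

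**Working it through.** **Inputs.** MRI, VO2R, bloodwork and MNSI weeks: Attachment A. N = 40, two-sided 5%, within-subject correlation 0.5, baseline means and Table 4: Section 9.4. Table 4 mean (SD) changes are BOLD 1.11 (1.26) exercise and 0.18 (1.42) control; PCr 10.61 (12.85) and 0.06 (8.53); MNSI 1.20 (1.78) and no control value.

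**1. The plan's own figures.** Detectable change at 80% power = SD × (1.960 + 0.842)/√40 = SD × 0.443.
- BOLD: 1.26 × 0.443 = 0.558; 0.558/3.24 = 17.2%.
- PCr: 12.85 × 0.443 = 5.69; 5.69/41.16 = 13.8%.
- MNSI: 1.78 × 0.443 = 0.789; 0.789/5.2 = 15.2%.

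All three lie within the stated 10% to 18%. The phase differences are 1.11 − 0.18 = 0.93 (BOLD) and 10.61 − 0.06 = 10.55 (PCr). Divided by the control change they give 5.2 and 176. These match Section 9.4, although the section labels them as percentages and they are multiples.

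**2. Intervals.** Control: 5 − 1 = 4 weeks. Exercise phase: 18 − 5 = 13 weeks, of which 10 are training. Excess: 13 − 4 = 9 weeks.

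**3. Bias of the Section 9.1/9.3 contrast.** With linear drift g per week and no exercise effect, the expected contrast is 13g − 4g = 9g.

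**4. Size from the documents' own data.** Assume that Table 4's control change is entirely linear drift over L weeks. L is not stated; the range used is 4 to 13. Then g = control change/L.

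| Outcome | 9g at L = 4 | 9g at L = 13 | Share of phase difference |
|---|---|---|---|
| BOLD | 0.18 × 9/4 = 0.405 | 0.18 × 9/13 = 0.125 | 44% to 13% of 0.93 |
| PCr | 0.06 × 9/4 = 0.135 | 0.06 × 9/13 = 0.042 | 1.3% to 0.4% of 10.55 |

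**5. The competing analysis.** With two scans, in Weeks 1 and 18, all 17 weeks of drift fall on exercise. On the same assumption, BOLD drift is 0.18 × 17/4 = 0.765 down to 0.18 × 17/13 = 0.235, or 69% to 21% of the 1.11 exercise change. For PCr it is at most 0.06 × 17/4 = 0.255, or 2.4% of 10.61.

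**6. Outcomes without a control change.** Attachment A has bloodwork in Weeks 1 and 18 and MNSI in Weeks 0, 1 and 18. Plasma ROS and MNSI therefore have no end-of-control value.

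**7. Scans in Weeks 6 and 17.** Intervals become 6 − 1 = 5 and 17 − 6 = 11 weeks, and the bias becomes 6g, one third smaller. On the step 4 assumption, BOLD falls to 0.18 × 6/4 = 0.27 (29%) down to 0.18 × 6/13 = 0.083 (9%).

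**8. Could the control change be scaled up?** The scaled contrast is Y3 − (1 + k)Y2 + kY1, with k = exercise interval/control interval. With equal SDs and correlation 0.5 at all three scans, its SD is √{0.5 × [1 + (1 + k)² + k²]} in baseline SD units.
- k = 1 (unscaled): √3 = 1.73; SE = 1.73/√40 = 0.27.
- k = 13/4: √14.81 = 3.85; SE = 0.61.
- k = 11/5: √8.04 = 2.84; SE = 0.45.

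**The case against.** **A different analysis may be the primary one.** Section 9.3.2 carries the primary-efficacy heading and has no phase contrast, so the 9-week figure would not apply. This stands as a limit on scope. It does not remove the problem, because under that text the untreated comparison disappears and step 5 applies.

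**The point does not reach every outcome.** Correct: it concerns MRI outcomes only.

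**A reader might infer that the design inflates false claims of benefit.** The documents do not support that. The only drift they describe is progression, which worsens outcomes, whereas the Section 9.2 hypotheses predict improvement. A two-year study suggests staggered entry, so season need not push all participants one way, and general activity is a covariate. Learning or regression to the mean would fall mainly in the first interval and could act in the opposite direction.

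**A reader might also attach a false-positive rate to an assumed drift.** The documents give no drift rate. Table 4's PCr control change of 0.06 indicates very little drift for that outcome. BOLD's 0.18 is larger, but its interval and preliminary sample size are not given, so it may be noise.

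**The 13 weeks is nominal.** The attachments page says the attachments are not part of the protocol. Section 4.7.2 requires a restart only when the control interval is "greater than 3-months between Step 2: Blood draw (section 6.4.1.2) and Post-non-exercise phase visit (section 6.4.3"), so a long control interval could shrink the gap. Its 4-month limit names no clear end visit. This is a reason to record dates.

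**The test-order asymmetry has no stated mechanism or size.** Also true. It is worth removing because it comes free with the rescheduling, but no bias should be claimed from it.

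**Conclusion.** The concern holds for MRI outcomes under the Section 9.1/9.3 comparison. The intervals are nominally 4 and 13 weeks, the order is fixed, and nothing in the model represents elapsed time, so linear drift g shifts the contrast by 9g in whichever direction the drift runs.

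Its size is unknown. If the preliminary control changes were pure linear drift over 4 to 13 weeks, it is negligible for PCr and possibly material for BOLD. That range rests on linearity, on an unstated preliminary interval, and on Attachment A's weeks being followed. Nothing comparable can be calculated from the documents for DTI or IDEAL-MRI.

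The supportable conclusion is that the contrast cannot attribute the MRI change to exercise alone. A reader might infer that it has been shown to be seriously biased, or that interval scaling would repair it. The first lacks a drift estimate, and the second fails on precision at N = 40. Equal intervals would not be a full remedy either, because the order would still be fixed. The study remains worth running; its schedule and claims should change.

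**What to change.** 1. **Move two existing scans.** Put the pre-exercise MRI in Week 6 and the final MRI in Week 17, each before that week's VO2R test, and leave the exercise weeks as they are. The MRI intervals become about 5 and 11 weeks, the excess falls from 9 to 6, and the test order matches. Week 17 is within the Section 6.4.4 window. State these weeks in Section 6.4, since the attachment is outside the protocol, and align the 4-week wording in Section 3.1. No scan is added. The cost is tighter booking on scanners that Section 4.5 already calls limited, plus a decision on whether the Week 18 bloods and MNSI move with the scan. The bias is reduced, not removed.

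2. **Reconcile the analysis sections.** Amend Sections 9.3.1 and 9.3.2 (and the scan count in Section 12.3) so that the three-scan phase contrast is the stated analysis for MRI outcomes. This is a text change.

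3. **Limit the claim.** Remove the cross-over label from the title. Replace the causal attribution in Section 9.3 with a statement that the change over the exercise period exceeded the change over a shorter, earlier untreated period. For ROS and MNSI, report an uncontrolled pre-post change only. The cost is a weaker conclusion, which is the one the design supports.

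4. **Record actual scan dates and report interval lengths.** Any interval-scaled contrast should be descriptive, with its imprecision stated (SE about 0.61 SD at 13:4 or 0.45 SD at 11:5, against 0.27 SD unscaled). It must not decide whether the conclusion stands.

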# 3.2 Study Endpoints

# 3.2.1 Primary Study Endpoints

Body mass index (BMI), glycosylated hemoglobin (HbA1c), and C-reactive protein will be assessed before and after the 10-week intervention, along with the following measures of neuropathic symptoms: 1) MNSI symptom questionnaire with yes/no responses to 15 items indicating the frequency and severity of neuropathic symptoms and Patient-Reported Outcomes Measurement Information System (PROMIS) Physical Function and Fatigue subscales, which are computer adaptive tools, will be used to assess symptoms related to physical disability and fatigue [52]; 2) MNSI physical exam score, to indicate abnormalities in the appearance of the feet, vibration sense, reflexes, and monofilament sensation; 3) Vibration Perception Threshold (VPT) will be assessed on the plantar aspect of the great toe [53] and Calf Muscle performance will be quantified as peak ankle plantarflexion torque at 60 degrees/sec [54]; 5) Plasma levels hydrogen peroxide as marker of ROS; 6) Lower leg muscle performance will also be assessed using the 9-item Physical Performance Test [54]; and 7) the Utah Early Neuropathy Scale, which is a physical exam specific to early sensory predominant polyneuropathy. Physical activity will be quantified using a wearable activity monitor (actigraph) [55]. Subjects will be required to wear the actigraph for at least a week.

The following outcomes will be assessed through multinuclear-MRI: 1) PCr resynthesis rate in the gastrocnemius (G) and the soleus (S) muscle groups, following a 90-s plantar flexion exercise during which resistance is applied at approximately 40% of the individual's maximum voluntary contraction (MVC); 2) Time-to-peak (TTP) of the BOLD signal in the G and S muscle groups; 3) Peak  $\Delta T2^*$  at 100% isometric MVC in the G and S muscle groups; 4) IMAT in the G and S muscle groups using IDEAL MRI; 5) Fractional anisotropy (FA) in the tibial nerve using DTI; 6) Apparent diffusion coefficient (ADC) in the tibial nerve using DTI.

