# 2 Objectives and Purpose

# 2.1 Primary Objective

The primary objective is to assess and compare the interventions (exercise versus control phase) in terms of the baseline to follow-up change in the following outcomes: 1) DTI, plasma ROS level, and the MNSI assessment of DPN symptoms (Aim 1); and 2) leg mitochondrial function, oxidative capacity (31P-MRI), peak MV response (BOLD-MRI), the proportion of fat-free muscle (IDEAL-MRI) and leg muscle strength (Aim 2).

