# 3.2.2 Secondary Study Endpoints

NA

Identification of baseline factors (e.g., age, MNSI [56], general activity) predictive of improvement, represented as the baseline to follow-up change in each outcome.

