# 9.2 Statistical Hypotheses

**Hypothesis 1a:** Exercise will improve peripheral nerve integrity (DTI fractional anisotropy will increase, and the apparent diffusion coefficient will decrease).

Hypothesis 1b: Exercise will decrease plasma ROS levels.

Hypothesis 1c: Exercise will improve DPN symptoms, assessed with the MNSI.

**Hypothesis 2a:** Exercise will increase leg mitochondrial function, as defined by an increase in oxidative capacity (measured using P-MRI).

**Hypothesis 2b:** Exercise will improve leg MV function, as defined by an increase in peak MV response (measured using BOLD-MRI).

**Hypothesis 2c:** Exercise will decrease intramuscular fat and increase levels of fat-free muscle (measured using IDEAL-MRI).

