# 9.3.2 Analysis of the Primary Efficacy Endpoint(s)

A matched-pairs Wilcoxon signed rank test will be applied to the within-subject change in each outcome among subjects demonstrating full compliance with the exercise program. Additionally, weighted analysis of covariance (ANCOVA) will be used to test the change in each outcome adjusting for the measured level of compliance using data from all subjects. The values of each outcome at

CONFIDENTIAL

baseline and follow-up for all subjects will be the dependent variable and the ANCOVA model will include time (baseline versus follow-up) as the within-subject factor of interest covariates, the measure of compliance as numeric covariate and an anonymized subject ID as a classification factor so that the comparison of times will be based on their within-subject difference. The secondary objective is to assess the extent to which exercise induced improvements in DTI outcomes are can be at least partially explained by reduction in ROS will be addressed using linear regression, The baseline to follow-up change in each outcome will be the dependent variable and the model will include the measure of compliance as a numeric factor and the within-subject change in ROS as the numeric factor of interest. A second regression will be conducted with baseline factors (e.g., age, MNSI, general activity) added to the model in order to identify factors predictive of improvement in each outcome.

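### Section 3.2.1 labels 22 measures primary with no lead outcome, and 9.3.2 opens with a full-complier test; no success rule or error control is stated

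*Combined protocol and SAP*

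**What the plan says.** **Endpoints.** Section 3.2.1 opens with "Body mass index (BMI), glycosylated hemoglobin (HbA1c), and C-reactive protein will be assessed before and after the 10-week intervention, along with the following measures". It then lists questionnaires, examination scores, performance tests, a plasma ROS marker, actigraphy and six MRI items, four of which are measured in two muscles. Nothing in the list is ranked. Under "3.2.2 Secondary Study Endpoints" the entry is NA; the text that follows concerns baseline predictors of improvement.

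**Objectives and hypotheses.** Section 2.1 names "DTI, plasma ROS level, and the MNSI assessment of DPN symptoms (Aim 1") and, for Aim 2, oxidative capacity, peak BOLD response, fat-free muscle and leg strength. Section 9.1 repeats this list with the aim to "assess and compare the interventions (exercise versus control phase in the same individual"). Section 9.2 states six hypotheses, 1a to 2c, for example "Exercise will improve DPN symptoms, assessed with the MNSI". None concerns leg strength.

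**Tests.** Section 9.3 gives a weighted paired t-test that "will be used to assess whether each outcome changed from baseline to follow-up as a result of the exercise intervention" and a weighted ANCOVA that "will be used to compare the time points in terms of the change in each outcome". Section 9.3.2, the only section headed as the primary efficacy analysis, begins "A matched-pairs Wilcoxon signed rank test will be applied to the within-subject change in each outcome among subjects demonstrating full compliance". It then adds a weighted ANCOVA on the values at both visits in all subjects. Section 9.3.4 states ITT with every subject included, weighted by compliance from 0 to 1.

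**Error level.** The only significance level is the two-sided 5% used for power in 9.4.

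**The concern.** A reader cannot tell which outcome, or which test in which population, answers each aim. The three lists disagree. BMI, HbA1c, CRP, PROMIS, VPT, the 9-item test, the Utah scale and BOLD time-to-peak are primary in 3.2.1 but appear in neither the objective nor the hypotheses. Leg strength is in the objective but has no hypothesis.

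The order of tests in 9.3.2 matters as well. A test restricted to full compliers selects subjects on behaviour after enrolment, and it stands first in the section that should carry the ITT result.

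At stake is what a primary result will mean. Section 1.3.2 presents establishing the efficacy of exercise as the benefit to society. Yet nothing in the plan prevents the report from leading with whichever primary measure, or whichever population, turns out significant.

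**Working it through.** **1. The plan's own figures.** Inputs from 9.4: n = 40, two-sided 5%, 80% power; exercise changes (mean, SD) of 1.11, 1.26 for BOLD, 10.61, 12.85 for PCr and 1.20, 1.78 for MNSI; baseline means 3.24, 41.16 and 5.2. A paired t-test (noncentral t) detects d = 0.454. As a percentage of baseline:

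- BOLD: 0.454 × 1.26 / 3.24 = 17.7%
- PCr: 0.454 × 12.85 / 41.16 = 14.2%
- MNSI: 0.454 × 1.78 / 5.2 = 15.5%

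All lie within the stated 10% to 18%. The anticipated changes are 34.3%, 25.8% and 23.1%, matching the stated 23% to 34%. So the power statement rests on each outcome being tested alone at 5%. The 10% end cannot be checked because Table 3 is broken in the text available.

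**2. The count in 3.2.1.**

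- BMI, HbA1c, CRP: 3
- MNSI questionnaire, PROMIS physical function, PROMIS fatigue: 3
- MNSI examination, VPT, calf torque, hydrogen peroxide, 9-item test, Utah scale: 6
- PCr rate, time-to-peak, peak ΔT2*, IMAT, each in two muscles: 8
- FA and ADC: 2

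The total is 22, or 23 with actigraphy. Counting MNSI once, PROMIS once and each muscle measure once gives 10 + 6 = 16. Sections 2.1/9.1 give seven domains (hypothesis 2a defines mitochondrial function as oxidative capacity), or eight tests if FA and ADC are separate. Section 9.2 gives six hypotheses.

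**3. Chance of at least one false positive** if any one of k null outcomes at two-sided 5% counted. Independent: 1 − 0.95^k. With common correlation ρ: 1 − ∫ φ(u) [Φ((c − √ρ u)/√(1−ρ)) − Φ((−c − √ρ u)/√(1−ρ))]^k du, with c = 1.96. The documents give no between-outcome correlation. The 0.5 in 9.4 is baseline against follow-up within one outcome, so ρ is assumed and shown over a range.

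| k | ρ = 0 | 0.3 | 0.5 | 0.7 | 0.9 |
|---|---|---|---|---|---|
| 22 | 68% | 57% | 44% | 30% | 16% |
| 16 | 56% | 48% | 37% | 26% | 15% |
| 8 | 34% | 30% | 25% | 19% | 12% |
| 7 | 30% | 27% | 23% | 18% | 11% |
| 6 | 26% | 24% | 21% | 16% | 11% |
| 2 | 9.8% | 9.5% | 9.1% | 8.3% | 7.0% |

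With 23 measures the independent figure is 69%. Simulated one-sample t-tests with n = 40 and 22 outcomes agree: 68%, 57%, 45% and 30% at ρ = 0, 0.3, 0.5 and 0.7.

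**4. Power at 2.5%,** the first Holm step with two aims (paired t, n = 40, unweighted, Table 4 inputs):

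- MNSI pre-post: 98.6% at 5%, 97.0% at 2.5%.
- PCr pre-post: 99.9% and 99.8%.
- PCr exercise change minus control change: mean 10.61 − 0.06 = 10.55; SD = √(12.85² + 8.53² − 2r × 12.85 × 8.53). The correlation r between the two phase changes is assumed. At r = −0.8, −0.5 and 0 the SD is 20.33, 18.64 and 15.42. Power is 89%, 94% and 99% at 5%, and 82%, 89% and 97% at 2.5%.

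**The case against.** The best defence is that this is a single-centre mechanistic study that nowhere claims family-wise control, and that 2.1 and 9.2 show what it is designed to test. Unadjusted results, labelled as such, would be legitimate. Part of this stands: the plan makes no claim that it breaks, and the shorter lists give smaller figures. But those lists are unranked too. Six tests still give 11% to 26% over the correlations examined, and the plan does not label its results unadjusted or exploratory; it calls them primary.

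Three stronger readings are tempting and are not supported.

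- A reader might infer that the trial has a false-positive rate of 68%, or of 30% to 57%. Those figures need a rule that any one result counts, which the plan never states, and a correlation that it does not give. Neither 30% nor 57% is a bound.
- A reader might infer that four primary tests compete. Only 9.3.2 is headed as the primary-endpoint analysis, and it has two. Section 9.3, with its matching factors and intervention groups, reads like text for a parallel-group design. The fault is that it is not reconciled with 9.3.2.
- A reader might want a figure for choosing the better of the complier and all-subject tests. It would depend on the share of full compliers and on the compliance weights. Section 9.3.4 lets the weights run from 0 to 1 and gives no distribution, so none is offered here.

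**Conclusion.** The point stands as a defect of specification. Twenty-two measures (23 with actigraphy) are labelled primary, the three lists do not match, and the primary-efficacy section leads with a complier-only test against the stated ITT principle. No success rule or error control appears. The size is conditional: under an any-one-counts reading with no real effect, 68% for 22 independent measures and 57% to 30% at assumed correlations of 0.3 to 0.7; for the six hypotheses, 26%, and 24% to 16%. Every list examined exceeds 5% at every correlation examined. This should be corrected before analysis. It does not show that any result will be false, or that the sample is too small.

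**What to change.** - Name one primary outcome per aim, chosen by the investigators from 2.1, and specify the MNSI part or the muscle where relevant.
- Decide each by one named test in all enrolled subjects. Relabel the full-complier Wilcoxon and the remaining tests as sensitivity analyses.
- Make the other 3.2.1 measures secondary or exploratory, reported with confidence intervals.
- Either control two-sided 5% across the two aims (Holm, for example), or state that each aim is tested separately at 5% and that the chance of an error in either is then about 7% to 10%.
- Align the Protocol Summary endpoint row, 2.1, 3.2.1, 3.2.2, 9.1, 9.2, 9.3, 9.3.2, 9.3.3 and 9.4.

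Conditions on the choice: if an MRI phase contrast is chosen, the scan count must first be reconciled (three in 1.2, 3.1 and Attachment A; two in 9.3.1 and 12.3), because that contrast exists only with three. MNSI pre-post does not make the exercise-versus-control comparison in 2.1, and Table 4 has no MNSI control value, so 2.1 would have to say so. A DTI outcome would need power inputs that the documents do not give.

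Cost: a text amendment with IRB approval (11.2), and no new visit for MNSI or PCr pre-post. The other outcomes lose primary status. Testing at 2.5% costs 1.6 points of power for MNSI pre-post and about 0.1 for PCr pre-post. For the PCr phase contrast power falls from 89-99% to 82-97% over the assumed correlations.
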